1. Prevalence of low QRS voltages in athletes and young non-athletic population on ECG analysis.
2. Prevalence of myocardial fibrosis in the young athletic and non-athletic population with low QRS.

Exploratory secondary outcomes:

- The proportion of individuals with low QRS complexes and myocardial fibrosis with rare protein altering variant in a cardiomyopathy gene.
- Exercise related ventricular premature beats or a ventricular premature beat burden of > 500 beats on a Holter monitor.

POPULATION 240 total study population: 60 athletes with low QRS voltage and 60 age and sex matched control group of athletes with normal QRS voltage, 60 non-athletes with low QRS voltage and 60 sex and age matched controls with normal QRS voltage

ELIGIBILITY Inclusion criteria for athletes and non-athletes with low QRS complexes:
Asymptomatic and body mass index <30.

Exclusion Criteria for Controls and Athletes: Individuals with cardiac symptoms; past medical history of cardiac disease; family history of SCD <40 years old or cardiomyopathy; previous myocarditis; lung disease; individuals with pacemakers, defibrillators; pregnant women; advanced kidney and/or liver disease; no known thyroid disease, T-wave inversion or other training unrelated ECG changes, significant valvular heart disease or intra-cardiac shunt on echocardiography.

DURATION 2022- 2027

1. INTRODUCTION

1.1. BACKGROUND

Low QRS Voltages in the Limb Leads in the general population: There is limited evidence in the literature that low QRS voltages (defined as QRS amplitude of <0.5mV in the limb leads) may be associated with left ventricular myocardial fibrosis and a predisposition to serious ventricular arrhythmias and SCD.^{1,2,5} Low QRS voltages on the 12-lead ECG are thought to reflect conditions that impair the transmission of electrical signals in the heart. The prevalence of low QRS complexes in the general population is between 0.3-2%.⁵⁻⁸ However, this includes individuals with chronic obstructive pulmonary disease, undiagnosed hypothyroidism, obesity, large pleural and pericardial effusion, severe left ventricular systolic dysfunction and infiltrative cardiomyopathies, which are also associated with low voltages.^{6,7,17-20,9-16} **The prevalence of low QRS voltages and their significance in young healthy individuals (17-35 years old) is not fully understood.**

Low QRS Voltages in the Limb Leads in Athletes: Sudden cardiac death (SCD) is one of the leading causes of death in athletes.²¹⁻²³ The majority of deaths are attributable to hereditary, structural or electrical pathologies which can be identified by abnormalities on the resting 12-lead ECG. Distinguishing physiological changes due to regular physical training resulting from increased vagal tone and increased chamber size and wall thickness²⁴ from those of potentially life threatening cardiac conditions can be challenging. The 2010 European Society of Cardiology recommendations for ECG interpretation in athletes²⁵ and the more recent international recommendations²⁶ provide a clear guide to aid ECG interpretation in athletes and are supported by a growing evidence base²⁴.

Low QRS voltages (<0.5mV in the limb leads and <1.0 mV in the precordial leads) do not feature in the current international recommendations²⁷ due to a lack of robust evidence. In a recent study in Italian competitive athletes demonstrated that the prevalence of low QRS voltages was 1.1%.⁵ Five athletes with low QRS voltages and exercise induced arrhythmias underwent CMR showing biventricular arrhythmogenic cardiomyopathy or idiopathic myocardial scar in two individual. In another study involving Italian Olympian athletes demonstrated that the prevalence of low QRS voltages of 4%.²⁸ All athletes were investigated with ECG, echocardiography, maximal exercise test and 24-hour Holter recording. The researchers did not identify any correlation between low QRS voltages and left ventricular morphology on echocardiography although premature ventricular beats were more frequent in athletes with low QRS voltages compared with athletes with normal QRS voltages (39% vs 7%). Furthermore, no cardiac events were recorded over a follow-up period of 5±2 years. **The main limitation of this study is that athletes with low QRS voltages did not have CMR for the assessment of myocardial fibrosis.** In a study of 35 competitive athletes with isolated non-ischaemic LV scar by CMR and ventricular arrhythmias, Zorzi et al reported that 20% of this cohort exhibited low QRS voltages.⁴ **A larger study in athletes and healthy individuals with low QRS voltages versus a control population using CMR is required.**

Cardiovascular Magnetic Resonance in Athletes: There has been a substantial rise in the use of CMR for assessing athletes with ECG repolarisation changes. CMR has high reproducibility and provides detailed tissue characterisation. CMR with gadolinium contrast provides the unique ability to detect myocardial inflammation and fibrosis. T1 mapping enables the detection of interstitial fibrosis and T2 mapping detects myocardial oedema. Assessment of extracellular volume (ECV) provides quantitative assessment of cellular vs

extracellular composition. Such techniques can play a pivotal role in understanding tissue changes contributing to low QRS voltages.

1.2. RATIONALE FOR CURRENT STUDY

The limitations of the above studies described are that not all athletes with low QRS voltages undertook a CMR evaluation to determine sensitivity, specificity, and positive predictive value of disease prediction. Therefore there is a need for a larger study in athletes and healthy individuals with low QRS voltages versus a control population using CMR to further evaluate the findings on these studies.

We postulate that left ventricular lateral/inferior wall subepicardial wall myocardial fibrosis in young individuals and athletes manifests as small QRS voltages on the ECG. In turn, myocardial fibrosis in athletes and young non-athletic individuals may reflect a pathogenic or likely pathogenic mutation in genes associated with cardiomyopathies. Such an approach to evaluating low QRS voltages in athletes should ultimately help determine the precise significance of small QRS complexes in young apparently healthy non-athletic individuals and athletes. The outcomes will facilitate the development of new recommendations on ECG interpretation in young individuals and athletes and identify young people at risk of SCD.

We hypothesise that in athletes and non-athletic subjects aged 17-35 years old with low QRS voltages: 1. The prevalence of myocardial fibrosis is greater. 2. The prevalence of known/likely pathogenic mutations in genes associated with DCM/AVC is greater.

2. STUDY OBJECTIVES

Primary objective is to investigate the prevalence and significance of low QRS voltages in young healthy individuals and athletes aged 17-35 years old.

This study will also aim to inform updated current international recommendations on ECG interpretation in athletes. The results of this study will have an impact on athletes worldwide, even if an ICD was not implanted there are several measures that would mitigate the risk of sudden death such as advise to abstain from vigorous exercise, regular surveillance for risk stratification, screening of first-degree relatives to identify others who may be affected.

Study Design and Period: Cross sectional, observational study over 5 years

3. STUDY DESIGN

Cross sectional observational study

Study Population: 60 apparently healthy athletes and 60 apparently healthy non-athletes.

Controls: The control population will consist of 60 sex and aged matched healthy athletes with normal QRS complexes (paired for the athlete group with low QRS complexes) and 60 non athletes (paired for the non-athlete group with low QRS complexes).

Study duration: 60 months

3.1. STUDY OUTCOME MEASURES

Primary outcomes: 1. Prevalence of low QRS voltages in athletes and young non-athletic population on ECG analysis. 2. Prevalence of myocardial fibrosis in the young athletic and non-athletic population with low QRS.

Exploratory secondary outcomes: 3. The proportion of individuals with low QRS complexes and myocardial fibrosis with rare protein altering variant in a cardiomyopathy gene. 4. Exercise related ventricular premature beats or a ventricular premature beat burden of > 500 beats on a Holter monitor.

PLANNED SUBGROUP ANALYSIS: We will investigate whether concomitant exercise related ventricular premature beats or a ventricular premature beat burden of > 500 beats on a Holter monitor predict myocardial fibrosis in athletes and non-athletes with low QRS complexes.

4. PARTICIPANT ENTRY

4.1. PRE-REGISTRATION EVALUATIONS

12-lead ECG: A standard 12-lead ECG will be performed using either a MAC 5000 or MAC 5500 digital resting ECG recorder

Blood Test: A thyroid function test will be performed to ensure participants meet the inclusion criteria and do not have thyroid disease as a potential confounding factor to this study.

4.2. INCLUSION CRITERIA

Inclusion criteria: athletes and non-athletes with low QRS complexes who are asymptomatic and with a body mass index <30.

4.3. EXCLUSION CRITERIA

Exclusion Criteria for Controls and Athletes: Individuals with cardiac symptoms; past medical history of cardiac disease; family history of SCD <40 years old or cardiomyopathy; previous myocarditis; lung disease; individuals with pacemakers, defibrillators; pregnant women; advanced kidney and/or liver disease; no known thyroid disease, T-wave inversion or other training unrelated ECG changes, significant valvular heart disease or intra-cardiac shunt on echocardiography.

4.4. WITHDRAWAL CRITERIA

Study participants can decide to withdraw from the study at any point

5. ADVERSE EVENTS

5.1. DEFINITIONS

Adverse Event (AE): any untoward medical occurrence in a patient or clinical study subject.

Serious Adverse Event (SAE): any untoward medical occurrence or effect that:

- **Results in death**
- **Is life-threatening** – refers to an event in which the subject was at risk of death at the time of the event; it does not refer to an event which hypothetically might have caused death if it were more severe

- **Requires hospitalisation, or prolongation of existing inpatients' hospitalisation**
- **Results in persistent or significant disability or incapacity**
- **Is a congenital anomaly or birth defect**

Medical judgement should be exercised in deciding whether an AE is serious in other situations. Important AEs that are not immediately life-threatening or do not result in death or hospitalisation but may jeopardise the subject or may require intervention to prevent one of the other outcomes listed in the definition above, should also be considered serious.

5.2. REPORTING PROCEDURES

All adverse events should be reported. Depending on the nature of the event the reporting procedures below should be followed. Any questions concerning adverse event reporting should be directed to the Chief Investigator in the first instance.

5.3.1 Non serious AEs

All such events, whether expected or not, should be recorded- it should be specified if only some non-serious AEs will be recorded, any reporting should be consistent with the purpose of the trial end points.

5.3.2 Serious AEs

An SAE form should be completed and emailed to the Chief Investigator within 24 hours. However, relapse and death due to an pre-existing condition, and hospitalisations for elective treatment of a pre-existing condition do not need reporting as SAEs.

All SAEs should be reported to [name] where in the opinion of the Chief Investigator, the event was:

- 'related', ie resulted from the administration of any of the research procedures; and
- 'unexpected', ie an event that is not listed in the protocol as an expected occurrence

Reports of related and unexpected SAEs should be submitted within 15 days of the Chief Investigator becoming aware of the event, using the NRES SAE form for non-IMP studies. The Chief Investigator must also notify the Sponsor of all related and unexpected SAEs. Local investigators should report any SAEs as required by their Local Research Ethics Committee, Sponsor and/or Research & Development Office.

Contact details for reporting SAEs

[contact]

CI email (and contact details below)

[contact]

Fax: N/A

Please send SAE forms to: [contact]

[contact] (Mon to Fri 09.00 – 17.00)

6. ASSESSMENT AND FOLLOW-UP

Participants who require ongoing clinical surveillance will be followed up in the specialist services at Royal Brompton Hospital. Individuals living afar will be referred to their primary care physician to instigate a formal referral to the relevant local specialist clinic.

Any relevant incidental findings on the cardiac MRI that is directly not related to the heart would be referred to the primary care physician for appropriate investigations and onward referral if required.

LOSS TO FOLLOW UP: To minimise loss to attendance there will be telephone and written communication during and after investigation. NHS details will be obtained from athletes so that GPs can be contacted for up-to-date details should participants be uncontactable.

END OF THE STUDY: The study will be completed following completion of all investigations as outlined in the study protocol, availability and analysis of data including genetic results on all 240 subjects (120 athletes and 120 young individuals). The pre-planned date for completion is 30 November 2025.

7. STATISTICS AND DATA ANALYSIS

The study to contain 240 participants as per the power calculation below.

POWER CALCULATION:

Athletes: Given a 4% prevalence of low QRS complexes in athletes²⁸ a sample of 2,500 athletes' ECGs would be expected to yield 100 cases of athletes with low QRS. In a study by Zorzi et al⁴, 20% of athletes with myocardial fibrosis exhibited low QRS complexes in the limb leads, while the athletes with normal QRS had no myocardial fibrosis. Based on these parameters, for a power of 90% and 5% significance, a sample size of 55 athletes with low QRS complexes and 55 athletes with normal QRS is required to detect a difference in proportion of myocardial fibrosis. Allowing for a 5% exclusion rate following eligibility, we will recruit 60 athletes with and 60 athletes without low QRS complexes for further investigations.

Young Population: Given a 2% prevalence of low QRS complexes in the general population and taking into consideration that 36.5% of the UK population is young (aged 14-44 years old), a review of 12,000 young individuals' ECGs would be expected to yield 88 cases with low QRS. Again, using the study by Zorzi et al⁴, and assuming these parameters to hold in the general population of young people, for a power of 90% and 5% significance, a sample size of 55 young people with low QRS complexes and 55 young people with normal QRS is required to detect a difference in proportion of scar. Allowing for a 5% exclusion rate following eligibility, we will recruit 60 young people with and 60 young people without low QRS complexes for further investigations.

Data and all appropriate documentation will be stored for a minimum of 10 years after the completion of the study, including the follow-up period.

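### The power calculation uses the share of scar athletes with low QRS (20%) as the fibrosis rate in low-QRS athletes, against an unsourced 0%, so the 90% power is unsupported in both strata

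*Combined protocol and SAP*

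**What the plan says.** Section 7 of the combined protocol and SAP fixes the total from this calculation: "The study to contain 240 participants as per the power calculation below". For athletes, the inputs taken from the cited scar study are that "20% of athletes with myocardial fibrosis exhibited low QRS complexes in the limb leads, while the athletes with normal QRS had no myocardial fibrosis". From these, with the significance level set at 5% and the power at 90%, the plan concludes that "a sample size of 55 athletes with low QRS complexes and 55 athletes with normal QRS is required to detect a difference". The difference meant is between the proportions with fibrosis. A 5% allowance for exclusions takes this to 60 per group. The non-athlete calculation reaches the same 55 and 60 by "assuming these parameters to hold in the general population of young people".

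Section 1.1 describes the same source: "In a study of 35 competitive athletes with isolated non-ischaemic LV scar by CMR and ventricular arrhythmias", for which the authors "reported that 20% of this cohort exhibited low QRS voltages".

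The comparison being powered is the first hypothesis in section 1.2, that among people with low QRS "The prevalence of myocardial fibrosis is greater".

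**The concern.** The hypothesis compares fibrosis prevalence between people with low QRS and people with normal QRS. Its power depends on P(fibrosis | low QRS) and P(fibrosis | normal QRS). The cited cohort was selected for having scar, so it can supply only P(low QRS | fibrosis). The two conditional probabilities are different quantities and can differ widely.

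The comparator has its own problem. If every member of the cohort had scar and 20% had low QRS, the other 80% had scar without low QRS. As worded, the statement that normal-QRS athletes had no fibrosis cannot describe that cohort, and the plan names no other group.

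This calculation is the only justification given for 240 participants and the only statement of what the fibrosis comparison can detect in either stratum. If the study finds no clear difference, readers will rely on a 90% figure that has no supporting input.

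**Working it through.** **Inputs.** Section 7: 5% significance (sidedness not stated), 90% power, 20% and 0%, equal groups, 5% exclusions, low-QRS prevalence of 4% in athletes and 2% in the general population. Section 1.1: 35 athletes, all with scar, 20% with low QRS; low-QRS prevalence of 1.1% in another athlete study and 0.3–2% in the general population.

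**Step 1: reproduce 55.** Take p1 = 0.20, p2 = 0, mean 0.10, two-sided 5%.

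- Pooled normal formula: n0 = [1.960 × √(2 × 0.10 × 0.90) + 1.282 × √(0.20 × 0.80 + 0)]² / 0.20² = (0.8315 + 0.5126)² / 0.04 = 45.2.
- Continuity-corrected: n = (n0/4) × [1 + √(1 + 4/(n0 × 0.20))]² = 54.7, i.e. 55.

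This matches the plan. Other pairs also round to 55 (30% v 5% gives 54.1), but 20% and 0% are the only rates in the sentence. The 20% was therefore entered as a fibrosis rate in low-QRS athletes.

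**Step 2: direction of the 20%.** 20% of 35 is 7 athletes with scar and low QRS, leaving 28 with scar and no low QRS. This gives P(low QRS | scar) = 7/35. With no scar-free athletes described, neither rate that the comparison needs can be obtained from it.

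**Step 3: sensitivity of the sample size.** With the same corrected formula, 20% v 1% gives 62.7 (63 per group), 20% v 2% gives 72.1 (73), and 20% v 5% gives just over 113.0 (114).

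**Step 4: power at the planned size.** 60 less 5% is 57 per group. The table gives exact power (%) of a two-sided 5% Fisher test, by full enumeration of two independent binomials. All rates are assumptions, since the documents give none by QRS group.

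| Low-QRS rate | Normal 0% | 1% | 2% | 3% | 5% |
|---|---|---|---|---|---|
| 30% | >99.9 | 99.8 | 99.2 | 98.2 | 93.9 |
| 25% | 99.8 | 98.5 | 96.1 | 92.5 | 82.0 |
| 20% | 98.1 | 92.6 | 85.3 | 77.0 | 59.4 |
| 15% | 87.5 | 73.6 | 60.4 | 48.6 | 30.1 |
| 10% | 51.1 | 36.1 | 25.1 | 17.3 | 8.0 |
| Low-QRS rate needed for 90% power | 15.7% | 18.9% | 21.6% | 23.8% | 27.9% |

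**Step 5: the 20% in its true direction (illustration only).** Let q be the low-QRS prevalence and f an assumed overall fibrosis prevalence, which the documents do not give. Then P(fibrosis | low QRS) = 0.20f/q and P(fibrosis | normal QRS) = 0.80f/(1 − q).

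- With q = 4%, the first is 5f, which equals 20% only if f = 4%. The comparator is then 0.80 × 0.04/0.96 = 3.3%, and power at 57 per group is 74%.
- With q = 4% and f = 2%, the rates are 10% v 1.7% and power is 28%.
- With q = 2% and f = 2%, the rates are 20% v 1.6% and power is 88%.
- With q = 2% and f = 3%, the rates are 30% v 2.4% and power is 99%.
- With q = 1.1% and f = 1%, the rates are 18.2% v 0.8% and power is 89%.

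**The case against.** The reversal itself is hard to dispute, but several points can be made for the plan.

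- **The 0% may have a source.** The cited study may have had a separate comparison group that section 1.1 does not mention. That cannot be excluded from the documents. Also, 28 of 35 is a share of scar cases, not a fibrosis rate in normal-QRS athletes: it shows the rate is not literally zero, not that it is large. Both points stand, which is why the request is to name the group and to remove the figure only if there is none.
- **There is some headroom.** On the plan's own inputs, exact power at 57 per group is 98.1%, not 90%. That absorbs a 1% comparator (92.6%) but not 2% (85.3%), and it does not help if the low-QRS rate is below about 16%.
- **Detectable differences follow from the group size alone.** This is true, as the last row of the table shows. What the plan lacks is any basis for treating such rates as plausible.
- **The primary outcomes in section 3.1 are prevalences, not a test.** This is also true, but section 7 claims power for the between-group difference and derives the 240 from it.
- **Step 5 relies on an assumed f** and on carrying the 20% from athletes selected for scar and arrhythmia to asymptomatic people. It shows only that power could fall on either side of 90%; the conclusion does not depend on it.

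**Conclusion.** The concern holds. A proportion conditional on fibrosis has been used as one conditional on low QRS, and it is paired with a 0% comparator that the plan's own account of the cohort contradicts as worded. The formula was applied correctly; the inputs do not support the result. The 90% power is therefore unsupported in athletes, and also in non-athletes, where the same inputs are assumed to hold.

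This does not show that the study is underpowered. At 57 per group, power exceeds 90% if fibrosis is present in 25% of low-QRS and up to 3% of normal-QRS participants, and is about 25% if the rates are 10% and 2%. The documents do not indicate where in this range the study lies. The figures assume independent groups, as does the formula that reproduces 55; the age and sex pairing in section 3 is not modelled. Because the sample size rests on this passage, it should be corrected before the plan is relied on.

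**What to change.** In section 7:

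1. Describe the 20% as the share of a scar cohort that had low QRS, and do not use it as a fibrosis rate in low-QRS athletes.
2. Name the group that supplies the 0%. If there is none, remove it.
3. Keep 60 per group. In both strata, replace the unconditional 90% with a power table over stated fibrosis rates, including non-zero comparators. The table above can be used, with a note that it assumes independent groups, a two-sided 5% Fisher test and 57 analysable per group.
4. State the precision for the second primary outcome, as exact two-sided 95% intervals. For example, 12/60 gives 10.8–32.3% and 0/60 an upper limit of 6.0%; after 5% exclusions, 11/57 gives 10.0–31.9% and 0/57 an upper limit of 6.3%.
5. Report the low-minus-normal difference in fibrosis prevalence in each stratum with an exact or score confidence interval, so that a null result can be read from the interval and not from the planned power.

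The cost is a reworded passage, one table and one reported interval per stratum, with no added participants or investigations. The drawback for the sponsor is that the power statement becomes conditional and is less favourable in many scenarios.

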8. REGULATORY ISSUES

8.1. ETHICS APPROVAL

The Study Coordination Centre has obtained approval from the Central London Research Ethics Committee (REC) and Health Research Authority (HRA). The study must also receive confirmation of capacity and capability from each participating NHS Trust before accepting participants into the study or any research activity is carried out. The study will be conducted in accordance with the recommendations for physicians involved in research on human subjects adopted by the 18th World Medical Assembly, Helsinki 1964 and later revisions.

